4.2 Exclusion Criteria

Subjects who meet any of the following criteria must be excluded from the study:

1. Patients with active (acute or chronic) liver disease other than NASH (e.g. viral hepatitis, genetic hemochromatosis, Wilson disease, alpha-1 antitrypsin deficiency, alcohol liver disease, drug induced liver disease) at the time of enrolment.
2. ALT or AST > 5 times ULN.
3. Abnormal synthetic liver function (serum albumin ≤ 3.5 gm%, INR > 1.3).
4. Known alcohol and/or any other drug abuse or dependence in the last five years.
5. Weight > 120 Kg
6. Known history or presence of clinically significant, cardiovascular, gastrointestinal, metabolic (other than diabetes mellitus), neurologic, pulmonary, endocrine, psychiatric, neoplastic disorder or nephrotic syndrome.
7. History or presence of any disease or condition known to interfere with the absorption, distribution, metabolism or excretion of drugs including bile salt metabolites (e.g. inflammatory bowel disease (IBD), previous intestinal (ileal or colonic) operation, chronic pancreatitis, celiac disease or previous vagotomy).
8. Weight loss of more than 5% within 6 months prior to enrolment.
9. History of bariatric surgery.
10. Uncontrolled blood pressure $BP \geq 150/ \geq 95$.
11. Non type 2 DM (type 1, endocrinopathy, genetic syndromes etc).
12. Patients with HIV.
13. Daily alcohol intake > 20 g/day (2 units/day) for women and > 30 g/day (3 units/day) for men.
14. Treatment with anti-diabetic medications other than at least one and no more than-three of the following medications: metformin, sulfonylurea, DPP-4 inhibitors, oral GLP-1 receptor agonists (semaglutide), SGLT-2 inhibitors, or TZDs
15. Fibrates and statins, not provided on a stable dose in the last 6 months.
16. Patients who are treated with valproic acid, Tamoxifen, methotrexate, amiodarone.
17. Chronic treatment with antibiotics (e.g. Rifaximin).
18. Homeopathic and/or Alternative treatments. Any treatment must be stopped before the screening period.
19. Uncontrolled hypothyroidism defined as Thyroid Stimulating Hormone $> 2X$ the upper limit of normal (ULN). Thyroid dysfunction controlled for at least 6 months prior to screening is permitted.
20. Patients with renal dysfunction: eGFR < 40 ml/min.
21. Unexplained serum creatinine phosphokinase (CPK) $> 3X$ the upper limit of normal (ULN). Patients with a reason for CPK elevation may have the measurement repeated prior to enrolment; a CPK retest $> 3X$ ULN leads to exclusion.

22. Subjects meeting criteria for contraindication for MRI – including the following:
 - History of severe claustrophobia impacting ability to perform MRI during the study, even despite mild sedation/treatment with anxiolytic.
 - Subjects with metal implants, devices, paramagnetic objects contained within the body and excessive or metal containing tattoos.
 - Subjects unable to lie still within the environment of the MRI scanner or maintain a breath hold for the required period to acquire images, even despite mild sedation/treatment with anxiolytic.
23. Subject participated in a clinical research study involving a new chemical entity within 4 weeks of study entry.
24. Known allergy to soy

4.3 Subject and Trial Discontinuation

Subjects may choose to withdraw from this study at any time for any reason without penalty of jeopardizing their health care or loss of benefits to which the subject is otherwise entitled.

Within the provisions of informed consent and good clinical judgment with respect to safety, every attempt will be made to have subjects complete the study. The following are reasons to terminate a subject's participation in the study:

1. Subject experiences an AE that in the judgement of the Investigator poses a significant risk to the subject for continued participation in the study.
2. Subject uses any medication that in the judgment of the Investigator poses a significant risk to the subject for continued participation in the study or that will interfere with the interpretation of the results of the study.
3. Subject becomes pregnant.
4. Significant protocol violation or noncompliance on the part of the subject or the Investigator.
5. Intercurrent illness that requires treatment that is not consistent with the protocol requirements, or intercurrent illness or the associated treatment that in the judgment of the Investigator poses a significant risk to the subject for continued participation in the study.
6. Subject wishes to withdraw for any reason.
7. Sponsor elects to end the study, or the Investigational Site elects to end the study at their site.
8. Any other reason that in the judgment of the Investigator poses unacceptable risk to the subject.

Subjects who withdraw from the study prior to treatment may be replaced. Subjects who are withdrawn and have received at least one treatment will not be replaced. Subjects who discontinue study drug treatment will not be replaced.

Except in cases of emergency, the Investigator should consult with the Sponsor and the Medical Monitor before removing the subject from the study. In some circumstances it may be necessary to temporarily interrupt treatment as a result of AEs that may have an unclear relationship to the IMP. The Investigator should obtain approval from the Sponsor and Medical Monitor before restarting IMPs that were temporarily discontinued for an AE.

In the event that a subject discontinues the study prior to completion, the date the subject is withdrawn and the reason for discontinuation will be recorded in the source documents and CRF. Although a subject will not be obliged to give his/her reason for withdrawing prematurely, the Investigator will make a reasonable effort to obtain the reason while fully respecting the subject's rights.

All subjects who are randomized and treated (i.e., received any amount of IMP) will be included in the safety analyses. Thus, every effort will be made to contact any subject who fails to attend any follow-up appointments/contacts, in order to ensure that he/she is in satisfactory health. If a subject withdraws from the study as a result of meeting discontinuation criteria after the start of IMP administration, reasonable efforts should be made to have the subject return for the early withdrawal evaluations (Section 3.5). Any subject withdrawn due to a suspected IMP -related AE should be followed until resolution or stabilization of the event.

If a subject becomes pregnant, IMP will be discontinued immediately, and the subject will be referred to an obstetrician/gynecologist experienced in reproductive toxicity for further evaluation and counseling. The subject will be followed until delivery or other termination of pregnancy for outcome.

Subjects may choose to withdraw authorization to use and disclose their PHI. Such withdrawal of authorization must be made to the Investigator in writing. Any PHI collected by the Investigator prior to the date of such withdrawal will continue to be used and disclosed.

The Sponsor has the right to terminate this study, and the Investigator/Investigational Site has the right to close the site, at any time, although this should occur only after consultation between involved parties. The Investigator or representative will notify the IRB in writing of a premature termination of a study or closure of Investigational Site or of a temporary halt of the study, including the reason of such an action and will send a copy of the notification to the Sponsor.

Events that may trigger premature termination of a study or closure of an Investigational Site include, but are not limited to, a new toxicity finding, a request to discontinue the trial from a regulatory authority, non-compliance with the protocol, GCP violations, slow recruitment/low enrollment, or change in development plans for the IMP.

If either of the criteria listed below is met, enrollment of new subjects and dosing of ongoing subjects will be temporarily stopped. The Investigator, Sponsor, and the Medical Monitor will discuss whether a lower dose or any additional treatment guidelines should be implemented, or if the trial should be permanently stopped. Any proposed changes to the protocol to address such findings will be submitted for review and approval by the IEC/IRB and the Competent Authority prior to re-starting the trial.

1. A death within 30 days after IMP administration where there is a reasonable possibility that the drug caused the event;
2. Two Grade 4 AEs where there is a reasonable possibility that the IMP caused the events.

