7.5.1 Routine Reporting of Adverse Events

All AEs, whether or not associated with the IMP that are observed by the Investigator, other Investigational Site personnel, or those reported by the subject will be recorded in the subject's source documentation and on the AE page of the CRF. Copies of the SAE CRF pages or an SAE listing generated based on the CRF pages will be submitted to the Sponsor at regularly scheduled intervals to allow the Sponsor to meet expedited regulatory reporting requirements under 21 CFR 312.32 and regular regulatory reporting requirements under 21 CFR 312.33.

For each AE, the following information will be entered in the CRF:

- Medical diagnosis of the event in standard medical terminology (if a medical diagnosis cannot be determined, a description of each sign or symptom characterizing the event);
- Date of onset of any new AE or worsening of a previously observed AE. For the days when the subject is in the clinic (Visit 2 to Visit 9), the time (based on a 24-hour clock) of onset should be recorded if available;
- Date of resolution of the event (or confirmation ongoing). For the days when the subject is in the clinic (Visit 2 to Visit 9), the time (based on a 24-hour clock) of resolution should be recorded if available;
- Whether the event is serious (per definition in Section 7.4), and if so, the reason it is considered serious;
- Severity of AE (per definition in Section 7.7);
- Assessment of the attributability of the AE to the IMP [per definition in Section 7.5];
- Whether the event is expected (per definition in Section 7.8);
- Action taken in treating the AE (including concomitant medications or therapies administered) and/or change in the IMP administration or dose (including whether the IMP was temporarily interrupted or discontinued);
- Outcome of AE (per definition in Section 7.9).

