7.7 Adverse Event Severity Assessment

The Principal Investigator will provide an assessment of the severity of each adverse reaction by recording a severity rating on the appropriate AE reporting page of the subject's CRF. Severity will be assessed according to the following scale:

Mild – events are usually transient and easily tolerated, requiring no special treatment and causing no disruption of the subject's normal daily activities.

Moderate – events introduce a low level of inconvenience or concern to the subject and may interfere with daily activities but are usually improved by simple therapeutic measures. Moderate experiences may cause some interference with functioning.

Severe – events interrupt the subject's normal daily activities and generally require systemic drug therapy or other treatment. They are usually incapacitating.

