8.2 Safety Evaluation

8.2.1 Adverse Events

AEs will be coded using the most current version of MedDRA. The severity of AEs will be graded according to NCI CTCAE version 4.03. AEs will be regarded as “pretreatment” if they occur during the Placebo run-in period. TEAEs are defined as any AE that starts or increases in severity after the first dose of IMP at Visit 3.

The incidence of TEAEs will be tabulated by MedDRA preferred term, system organ class, treatment group, severity, and assigned relationship to IMP. The incidence for each TEAE will be provided as the total number of subjects that experienced the TEAE, as well as the percentage of the population that this represents. If a TEAE is reported more than once for a given subject, the greatest severity and the worst-case attribution will be presented in the summary tables.

TEAEs will be listed for individual subjects, along with information regarding onset and end dates, onset time where available, severity, seriousness, relationship to IMP, action taken, and outcome. A similar listing will be prepared for the pretreatment AEs.

Pretreatment AEs and TEAEs that lead to withdrawal from the study will be separately listed and summarized. Similarly, separate tabulations and listings will be prepared for pretreatment and treatment-emergent SAEs.

Descriptive statistics will be generated as appropriate (i.e., frequency for categorical data). Inferential statistical analysis comparing the AE data between Active treatment and Placebo is not planned.

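### The halt after two related Grade 4 AEs and the planned severity table both need a CTCAE grade that the CRF severity rating does not record

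*Combined protocol and SAP*

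**What the plan says.** Section 4.3 has two criteria that pause the trial: a death plausibly caused by the drug, and "Two Grade 4 AEs where there is a reasonable possibility that the IMP caused the events". The second names no grading scale or version.

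Severity is then defined in three places:

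- **Section 7.7**, to which the CRF entry in Section 7.5.1 points, has the investigator assess severity "by recording a severity rating on the appropriate AE reporting page". The scale has three unnumbered categories: Mild, Moderate and Severe.
- **Section 8.2.1** says "The severity of AEs will be graded according to NCI CTCAE version 4.03". It then plans the main safety table: "The incidence of TEAEs will be tabulated by MedDRA preferred term, system organ class, treatment group, severity, and assigned relationship to IMP".
- **Section 7.3.1** uses CTCAE version 5.0 for hypoglycaemia. It gives four glucose bands, the last being Life Threatening at below 30 mg/dL.

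Section 7.5 makes hypoglycaemic events AEs that go on the CRF, so Sections 7.3.1, 7.7 and 8.2.1 all apply to them. The protocol text contains no conversion between these scales, and it does not say which one Section 4.3 uses.

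**The concern.** A rule that pauses dosing has to be run while dosing continues, from something that is recorded at the time. Here the recorded severity rating stops at Severe, so it has no value that means Grade 4. Section 8.2.1 does call for CTCAE grades, but it sits in the analysis section and does not say who assigns the grade, when, or how it follows from the CRF rating.

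Two things depend on this. One is the pause in Section 4.3. The other is the severity table for the primary endpoint, which is safety. Section 8.2.1 shows each subject's greatest severity for a repeated event, so the scale used changes what the table reports.

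**Working it through.** The plan gives no operating characteristic for the halting rule, so there is no figure to reproduce. The check is a comparison of the sections, with some counting.

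**1. The scales side by side**

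| Section | Applies to | Scale | Grade 4 available? |
|---|---|---|---|
| 4.3 | Trial pause | Grade, no scale named | Required |
| 7.5.1 and 7.7 | Every AE, on the CRF | Mild, Moderate, Severe (3 levels) | No |
| 7.3.1 | Hypoglycaemia | CTCAE 5.0 by glucose (4 levels) | Fourth level is Life Threatening, not labelled Grade 4 |
| 8.2.1 | AEs in the analysis | CTCAE 4.03 | Yes, if someone assigns it |

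Section 7.7 has no numbered grades, so Grade 4 in Section 4.3 is best read as a CTCAE grade. Levels in 7.3.1 minus levels in 7.7: 4 − 3 = 1. The level without a counterpart is the top one, which is the one the halt needs. A Severe rating cannot be split afterwards into Grade 3 and Grade 4 without going back to the event itself.

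**2. The route that does not use the severity rating**

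Section 7.4 makes a life-threatening event serious. Section 7.5.2 sends serious AEs to the sponsor or its delegate within 24 hours, and does the same for AEs that are otherwise medically significant. Most Grade 4 events should arrive this way.

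**3. One event traced through: glucose below 30 mg/dL, corrected at home with juice or tablets**

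- Section 7.3.1: Life Threatening.
- Section 7.7: Moderate is possible, since such events "may interfere with daily activities but are usually improved by simple therapeutic measures". Severe is also possible. Neither is a Grade 4.
- Section 7.4: serious if the investigator judges that a criterion is met, and not otherwise.
- Section 7.5.2: 24-hour notice if the event is judged serious or otherwise medically significant.
- If it is judged neither, Section 7.5.1 sends only SAE pages or listings to the sponsor. Section 9.2 has CRFs completed visit by visit, then scanned and mailed, with no deadline stated.
- Section 3.7: the patient telephones the site, so the site should know promptly. That call does not go to the sponsor.
- The patient-level stop in Section 3.7 needs three or more values below 50 mg/dL within 12 hours, so a single low reading does not meet it.

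**4. Where the count has to be made**

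Sites from Section 8.1: Israel 2, Belgium 3 or 4, USA 2. Total: 2 + 3 + 2 = 7, or 2 + 4 + 2 = 8. The threshold is 2 events among up to 40 patients. The two events can occur at different sites, so the count has to be assembled centrally. One event not counted is 1/2 of the threshold.

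**5. The severity table**

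The table is planned in CTCAE grades and the prescribed CRF rating is on the 7.7 scale. It cannot be built from that rating without regrading each event.

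The documents give neither an expected rate of related Grade 4 AEs nor the share that would escape 24-hour reporting, so the chance of a late halt cannot be calculated.

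**The case against.** The best defence has four parts.

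- **Grade 4 can only mean CTCAE, and Section 8.2.1 says AEs are graded by CTCAE.** This is accepted as the meaning. It does not put the grade on the CRF, where Section 7.5.1 asks for the 7.7 rating.
- **The halt does not depend on the 7.7 rating, because 24-hour reporting covers life-threatening and medically significant events.** This largely stands. For the glucose example to be missed, the investigator would have to find it neither serious nor medically significant, despite the label in Section 7.3.1. The outpatient exclusion in Section 7.4 does not help that along, since it covers only events that already meet no seriousness criterion. Still, seriousness is a separate judgement from grade, and Section 4.3 counts grades.
- **Section 7.3.1 is the specific rule for hypoglycaemia and governs there.** This is a fair reading. It leaves every other AE without a recorded grade, and it cites a different CTCAE version from Section 8.2.1.
- **A separate SAP or CRF guide may hold a mapping.** Section 8 does defer detail to an SAP, and Section 7.5 requires a description of each event from which a grade could be worked out later. That could rescue the table. A rule that pauses dosing should be workable from the protocol that the sites follow.

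A reader might infer more than the documents support. The halt is not inoperable, because of the 24-hour route. Nor is it free of discretion: both criteria in Section 4.3 need a causality judgement, and the same section lets the investigator withdraw a patient for an AE that poses significant risk. The band from 55 to below 70 mg/dL is Mild in Section 7.3.1 but treated under Section 3.7, while Mild in Section 7.7 means "requiring no special treatment and causing no disruption". That is at most an untidiness in rating and has no bearing on a Grade 4 count. The spacing of visits does not measure the delay either, since the patient telephones the site and monitoring contacts may also bring the event to light.

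**Conclusion.** The inconsistency is real and should be fixed. Two stated rules set different severity scales for the same AEs, and the CRF severity rating supplies neither the Grade 4 count in Section 4.3 nor the CTCAE-graded table in Section 8.2.1.

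For the table, the mismatch affects every AE until the events are regraded. For the halt, the remaining risk is narrow: a late or inconsistent count for a Grade 4 event judged neither serious nor otherwise medically significant. Such events should be few, but with a threshold of two a single one is half the count.

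This rests on reading Grade 4 as CTCAE Grade 4, on treating the Life Threatening glucose band as its equivalent, and on there being no mapping in a document outside the text available. The mismatch between scales is certain from the page. How often it would delay the halt is unknown.

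**What to change.** 1. Replace the Section 7.7 scale with CTCAE grades 1 to 5 in one stated version, entered on the CRF when the AE is reported.
2. Cite that version in Sections 4.3, 7.3.1, 7.7 and 8.2.1.
3. State in Section 4.3 that a glucose below 30 mg/dL counts as Grade 4.
4. Require any Grade 4 AE to reach the sponsor within 24 hours, whether or not it is judged serious.

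The cost is a change to one CRF field, a protocol amendment with IRB and regulatory submission (Sections 10 and 11.2.3), brief retraining at the 7 or 8 sites, and a one-time grading of AEs already recorded. It adds no patients or visits.

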5 STUDY TREATMENT (IMP)

5.1 Description of Investigational Drug

ORMD-0801

Dosage form: 2 soft gelatin capsules per dose

Strength: 8 mg insulin per capsule

Description: API (recombinant human insulin USP), in Oramed's proprietary formulation [SBTI, disodium EDTA, fish oil, aerosil, and TWEEN 80] in capsules.

5.1.1 Packaging and Labeling

This study is an open-label study. All study medication will be shipped in bulk. The Investigational Site pharmacist will be responsible for dispensing the appropriate treatment period IMP.

Study medication will be dispensed to the site with instructions for when treatment can be administered. Medication containers and any unused capsules will be retained at the study site after the treatment phase of the study is complete.

The treatment packages will be labeled with the following information:

- Study number
- Patient ID
- Bottle ID
- Dosage Form/Content
- Directions for use, including route of administration
- Number of capsules in package
- Storage conditions
- Instructions to "keep out of reach of children"
- Caution: For Clinical Trial Use Only.
- Name of Sponsor

A separate label with the identical information will be provided with the label on the package for drug accountability purposes.

5.1.2 Storage and Handling

All IMP must be kept in an appropriate, secure area to prevent unauthorized access. All IMP is to be shipped under refrigerated conditions and stored in the original packaging at controlled temperature (36 to 46°F; 2 to 8°C). Excessive humidity should be avoided. Storage conditions will be monitored, and appropriate monitoring logs maintained as source data. Deviations from the established temperature, as well as the occurrence of excessive humidity, should be documented, and the Sponsor should be notified.

IMP should be handled and disposed, using proper procedures as defined by Investigational Site standard operating procedures (SOPs) for Investigational Drugs.

Investigator will be supplied with a sufficient amount of study medication in order to provide each subject with sufficient treatment. Site will document their inspection of shipments of study medication and notify the Sponsor of any breakage, shortage, or other adverse shipment events.

5.2 IMP Administration

5.2.1 Visit 3 to Visit 8

The treatment regimen (Active) will consist of a soft gelatin capsule containing 8 mg insulin, and 75 mg SBTI. Patients will take 2 capsules daily in the morning 30 to 45 minutes prior to breakfast and no later than 10AM. At Visit 2 (placebo) and at Visits 3, 6, 7, 8 (Active) capsules will be administered in the clinic. Blood samples and weights will be taken prior to dosing, after which the patients will take the drug, so he\she will be provided with a small snack to eat after 30 to 45 minutes.

